The U.S. Preventive Services Task Force identifies behavioral treatment including dietary, physical activity, and behavioral counseling components as a viable option for pediatric obesity treatment,² yet a key challenge is how to implement these programs to maximize access and participation. Summer (between school years) represents an opportunity for intensive intervention to change health behaviors and help children to lose weight. During the summer months, children gain weight at a more rapid pace^{3,4} and spend more time engaged in sedentary behavior⁵ compared to the school year. The American Diabetes Association launched Camp Power Up as a summer week-long day camp for youth who are obese and/or at high risk for developing type 2 diabetes. The camp will focus on wellness education, nutrition, physical activity, and obesity prevention. The purpose of the proposed study is to examine effects of Camp Power Up on children's weight status and their psychosocial health.

Inclusion and Exclusion Criteria

Children must meet the following eligibility criteria to participate in the study:

- Aged 6 to 14 years
- Enrolled in the ADA Camp Power Up

Number of Subjects

We plan to enroll up to 62 participants total. A total of 12 participants were enrolled in summer 2017 and an additional 50 are anticipated for summer 2018.

Recruitment Methods

All children selected to participate in the ADA summer camp program will be asked to participate in this study. The ADA anticipated enrollment of approximately 50 children for the one week session each summer (summer 2017, summer 2018). Recruiting efforts include, but are not limited to the institution's email listserv, social media posts, and flyer drops.

Study Timelines

The enrollment and participant's participation in the study will last approximately one week (five daytime sessions). The primary analyses will be completed by January 1, 2018 for the summer 2017 camp. The primary analyses for the summer 2018 camp will be completed by January 1, 2019.

Study Endpoints

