Participants 12 years of age and older will be given a written assent form to read and sign before participating in any study procedures. Participants 6-11 years of age will be read an assent script and asked to verbally assent before participating in any study procedures. Participants 9-11 years of age with a high reading comprehension and maturity level may give written assent, rather than verbal assent, if deemed appropriate by the investigator or research staff member performing the assent. The study procedures will be explained using age appropriate terms, and children will be given the opportunity to ask questions about the study.

Parent survey. Parents will be asked to complete a questionnaire that will provide information on the child's sociodemographic characteristics, including sex, date of birth, and parents' marital status, highest level of education, family income, occupation, and employment status, as well as brief medical history. Parents will report their own height, weight, age, and sex.

Anthropometric measurements. Height and weight of each child will be measured in a private setting with the child dressed in light clothing. Height will be measured to the nearest 1.0 cm using a portable stadiometer. Weight will be measured to the nearest 0.1 kg using high-precision electronic scale. Percent body fat will be recorded from this scale. Body mass index (BMI) z-score will be calculated based on the child's age, sex, height, and weight, then compared to the 2000 Centers for Disease Control and Prevention (CDC) Growth Charts to calculate percentile and z-score.

Surveys. A pre-test and post-test psychosocial questionnaire will be completed by each participant at the beginning (session 1 or orientation) and end (session 5) of the program. The questionnaire will collect information about lifestyle, including diet and physical activity habits, media use, and sleep.

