Weight Efficacy Lifestyle questionnaire (WEL; Summer 2017 and 2018): The WEL assesses self-reported eating habits and perceived self-efficacy in regards to eating and weight loss.⁹ The WEL consists of 20 items designed to measure five hypothetical dimensions of efficacy for weight management: availability, negative emotions, physical discomfort, positive activities, and social pressure. The items were slightly reworded to make them easily understandable to a pre-adolescent population. Good reliability and validity have been reported for the WEL in adult populations^{9,10} and adequate scale reliability in children ($\alpha=0.94$).¹¹

The Physical Activity Enjoyment Scale (PACES; Summer 2017 and 2018): The PACES is a 16-item measure of enjoyment during physical activity.¹²

The Body Image Assessment of Preadolescents (BIA-P; Summer 2017 only): The BIA-P is a reliable and valid measure of body image in children ages 6 to 14.^{13,14}

During summer 2018 camp only, children will be allowed to use the HD Expresso cybercycling stationary bicycles in the TReCC for 15 minutes each. Afterwards, they will complete a brief survey on their enjoyment and acceptability of the cybercycling.

(Summer 2018) One month after the conclusion of the camp, an optional post-camp celebration will be hosted at a local community center for all parents and camp participants. Participants' height and weight will be measured. Participants will be asked to complete a brief survey.

The following is the train schedule for procedures:

	PRE-VISIT	V1 Day 1	V2 Day 5	1 month Post- Visit
Consent	x			
Parent Questionnaire	x			
Assent	x			
Height		x	x	x
Weight		x	x	x
Child Questionnaires		x	x	x

Power analysis.

Difference scores will be calculated between initial and final assessment, and effect sizes will be calculated using linear mixed models to determine clinical significance of weight-related and psychosocial changes throughout the program. Acceptance and feasibility will be assessed by the number of participants enrolled and the number of camp sessions attended.

Data and Specimen Management

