Study Title: Feasibility of the Camp Power Up Program on Children's Body Weight and Quality of Life

NCT #: NCT03235440

Document date: September 1, 2020

We used SPSS to conduct paired t-tests to analyze any pre-to-posttest changes in health behaviors and psychosocial well-being outcomes. Cohen's d was computed as effect size to interpret the between time differences. Subsequently, we conducted repeated measure multivariate analyses of variance (RM-MANOVAs) to examine pre-to-posttest changes in health behaviors and psychosocial well-being outcomes by gender (boys vs. girls) and household income (\$50,000 as the split value). We further explored the pre-to-posttest changes in the outcomes (using gain scores: posttest – pretest data) by weight status (normal weight, overweight, obesity), but did not perform inferential statistical analysis due to the uneven sample sizes between the weight groups. Descriptive results including both raw and estimated marginal means were obtained to quantify and visualize group differences. Partial eta square (η^2) was reported as effect size from results from the RM-MANOVAs, while significance level was set to be $\alpha = 0.05$.

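### Change by household income is tested only through a $50,000 split that neither document justifies; if more than two income levels were recorded, the split discards roughly 20% to over 50% of the information on a graded income effect.

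*SAP*

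**What the plan says.** The SAP is a single paragraph. After the paired t-tests it states that "we conducted repeated measure multivariate analyses of variance (RM-MANOVAs) to examine pre-to-posttest changes" in health behaviours and psychosocial outcomes by gender and by household income, with "50,000 as the split value" for income. It adds that the "significance level was set to be" 0.05. It gives no reason for the $50,000 value and no count of children on either side. For weight status, the same paragraph withholds inferential testing because the groups were unequal in size.

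The protocol mentions income once, under Procedures Involved (Parent survey), where parents report "highest level of education, family income, occupation, and employment status". It does not say whether income is a dollar amount or a set of bands, or how many bands.

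The planned analysis, under Study Endpoints (Aim 1) and again under Power analysis, is difference scores, with the statement that "effect sizes will be calculated using linear mixed models to determine clinical significance of weight-related and psychosocial changes throughout the program". No income subgroup or cut point appears there. The Number of Subjects section says "We plan to enroll up to 62 participants total": 12 enrolled in 2017 and 50 anticipated for 2018.

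**The concern.** A split treats two families just either side of $50,000 as different, and treats all families on one side as the same. If the questionnaire recorded income more finely, that detail is lost from the only income analysis in the SAP.

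The sample is small, so this matters in two ways. A null result for income could reflect the split rather than the absence of a relation. A positive result could depend on where the cut was placed, and the reader has no stated reason for that placement. Without the counts on each side, the reader also cannot tell whether the imbalance that led the SAP to avoid testing by weight status applies to income as well.

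**Working it through.** The plan gives no power or information figure for the income analysis, and the protocol's Power analysis section contains no calculation. There is therefore nothing to reproduce, and the size has to be worked out under stated assumptions.

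**Inputs from the documents.** Maximum N = 62 (Protocol, Number of Subjects); alpha = 0.05 (SAP), taken as two-sided because sidedness is not stated.

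**Assumed.** The income distribution, the share p of families on one side of the cut, the recording format, and the correlation between income and change.

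**Step 1: information retained.** If change is linear in the income score, the split retains a fraction E of the information, where E is the squared correlation between the score and its 0/1 split. The loss is 1 - E.

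- Normal income: E = φ(z_p)² / [p(1-p)], where φ is the normal density at the p quantile. At the median, 0.3989² / 0.25 = 0.637.
- Uniform income: E = 3p(1-p). At the median, 3 × 0.25 = 0.75.
- Equally filled, equally spaced bands: E = p(1-p)D²/V, where D is the difference in mean score across the cut and V is the score variance. Five bands cut 40/60: 0.24 × 2.5² / 2 = 0.75. Four bands cut in the middle: 0.25 × 2² / 1.25 = 0.80. Five bands cut 20/80: 0.16 × 2.5² / 2 = 0.50.

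| Income assumption | Cut | Loss |
|---|---|---|
| Normal, continuous | 50/50 | 36.3% |
| Normal, continuous | 40/60 | 37.8% |
| Normal, continuous | 30/70 | 42.4% |
| Normal, continuous | 20/80 | 51.0% |
| Uniform | 50/50 | 25% |
| Uniform | 40/60 | 28% |
| 3 to 8 equal bands | best cut | 20-25% |
| Five equal bands | 20/80 | 50% |
| Six equal bands | first or last boundary | 57% |
| Bimodal shapes tried | centre | 19-32% |
| Exponential, linear in dollars | cuts tried | 35-52% |
| Lognormal (log-SD 0.5 to 1.0), linear in dollars | cuts tried | 39-73% |
| Two levels recorded, or true step at $50,000 | that level | 0 |

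In terms of children, a 50/50 split of normal income leaves 62 × 0.637 = 39.5 effective children. Equal bands at the best cut leave 62 × 0.75 = 46.5 to 62 × 0.80 = 49.6.

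**Step 2: illustrative power.** For one outcome, power ≈ Φ(atanh(ρ√E) × √(N-3) - 1.96), with ρ = 0.35 assumed and N = 62, so √59 = 7.681.

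- Continuous income (E = 1): atanh(0.35) = 0.3654; 0.3654 × 7.681 - 1.96 = 0.85; power 80%.
- 50/50 split (E = 0.637): ρ√E = 0.279; 0.2869 × 7.681 - 1.96 = 0.24; power 60%.
- 30/70 split (E = 0.576): ρ√E = 0.266; 0.2721 × 7.681 - 1.96 = 0.13; power 55%.
- A 20-25% loss (E = 0.80 to 0.75): power about 70% to 67%.

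The noncentral t gives 82.5%, 61.5% and 56.9% for the first three, and 73.5%, 52.2% and 48.0% at N = 50. The fall is about 20 points or more either way.

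**Step 3: if the cut had been searched for.** Simulation with N = 62, six equal bands and the best of five cuts gave a false-positive rate of about 17-18% instead of 5%. This is conditional on a search.

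**The case against.** A reader might infer that at least about a third of the information is always lost. That is not supported. The figure 1 - 2/π = 36% is a floor only for normal, continuously recorded income with a linear relation to change, and the documents establish none of these. If the alternative is an ordered band score, the right comparison is split against bands. Even with underlying normal income, a 50/50 split keeps 0.637/0.907 = 70% of what six bands keep, a 30% loss. This objection stands, so the loss has to be given as a range.

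A reader might also infer that $50,000 was picked after looking at results. The SAP is in the past tense and dated September 2020, after the protocol's January 2018 and January 2019 dates for the primary analyses. That shows when the text was written, not how the cut was chosen. Nothing describes a search, and $50,000 is a round number. The 17-18% error rate therefore cannot be attributed to this trial.

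Three further points carry weight. The power figures are for one outcome, whereas the SAP's test is multivariate. The correlation of 0.35 has no source, and 62 is an enrolment ceiling. Income belongs to no aim or endpoint, the primary endpoint is change in body weight, and the income analysis follows the main paired tests. Finally, replacing an analysis already reported is itself post hoc unless labelled so.

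None of this supplies a reason for the cut or shows that the split is the better use of the data.

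**Conclusion.** The point holds in a limited form. The SAP tests change by income through one split that neither document justifies. The loss is about 20-25% against equally filled bands at the best cut, at least 36% under normal, continuous, linear income, and over 50% for cuts far from the centre. This rests on two assumptions: the questionnaire recorded more than two income levels, and the relation is roughly monotone. If either only two levels were recorded or the true relation is a step at $50,000, the loss is zero.

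The power fall from about 80% to 60% or 55% is an illustration at an assumed correlation of 0.35 and the maximum N, not an estimate for the SAP's own test. The consequence is confined to this secondary income analysis. It should be corrected, but the conclusions on body weight and on overall pre-post change do not depend on it.

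**What to change.** In the SAP, enter income as collected (ordered band score, or band midpoint) as a time-by-income term in the repeated-measures model. Report the trend for each outcome with a 95% CI. With two time points this equals regressing the gain score on the income score, so the interval is easy to obtain. Label it exploratory, and post hoc if it is added after the data were seen.

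Keep the $50,000 split as a secondary descriptive table with the number of children on each side. State why $50,000 was used, when it was chosen, and how the questionnaire recorded income.

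The cost is a few lines of SAP text and one re-run in SPSS on data already collected. The downside is that a trend assumes a roughly monotone relation and would describe a true threshold less well; the descriptive table partly covers that. If only two levels were recorded, no re-run is needed and a sentence saying so is enough.

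### The SAP's effect size for the gender and income RM-MANOVAs is unadjusted partial eta squared with no confidence interval; in its multivariate form an absent effect can look medium-sized

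*SAP*

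**What the plan says.** The SAP is a single paragraph. After the paired t-tests, it says that "we conducted repeated measure multivariate analyses of variance (RM-MANOVAs) to examine pre-to-posttest changes in health behaviors and psychosocial well-being outcomes". The grouping factors have two levels each: the child's gender, and family income split at $50,000. As to effect size, partial eta squared "was reported as effect size from results from the RM-MANOVAs, while significance level was set to be" the 5% level.

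The same paragraph says that raw and estimated marginal means were obtained as descriptive results, to put numbers on how the groups differ. It gives no confidence interval for a between-group difference and no bias-adjusted effect size. Four things are left open: whether the eta squared is the joint (multivariate) value or the per-outcome value, how many outcomes enter each model, how many children were analysed, and whether any small/medium/large benchmarks were applied.

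On sample size the protocol (Number of Subjects) gives only a ceiling: "We plan to enroll up to 62 participants total", made up of 12 enrolled in 2017 and 50 anticipated in 2018. On the lifestyle outcomes it says: "The questionnaire will collect information about lifestyle, including diet and physical activity habits, media use, and sleep" (Procedures Involved, Surveys).

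**The concern.** Partial eta squared cannot be negative, so sampling noise alone pushes it above zero. In the multivariate form the push grows with the number of outcomes and with falling sample size. In a study of at most 62 children with several outcomes per model, a value that a reader would call medium can arise when boys and girls, or the two income groups, changed by the same amount. Values from models with different numbers of outcomes are also not comparable with one another.

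Without an interval, a reader cannot tell whether a non-significant comparison excludes a difference worth knowing about. What is at stake is how the size of these secondary subgroup results is read.

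**Working it through.** The documents give no effect-size, power or precision figure to reproduce; the protocol's Power analysis section contains no calculation.

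**Inputs**
- N: at most 62 (protocol, Number of Subjects). The analysed N is not stated; 50 and 30 are shown as assumed smaller values.
- p: not stated. Assumed 4 if diet, physical activity, media use and sleep each give one health-behavior outcome; 3 if PedsQL, WEL and PACES (the scales used in both summers) each enter as one score; 7 if both sets share one model.
- Groups: two levels for gender and two for income, so one hypothesis degree of freedom each.
- Benchmarks of 0.06 (medium) and 0.14 (large): conventions, assumed. Neither document cites them.

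**Formula.** For a two-level factor acting on p change scores (the time-by-group effect), multivariate partial eta squared is 1 - Wilks' lambda. With no true effect and one factor in the model, it follows Beta(p/2, (N-1-p)/2), with mean p/(N-1).

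At N = 62: 3/61 = 0.049, 4/61 = 0.066, 7/61 = 0.115. Per outcome (p = 1): 1/61 = 0.016.

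| N | p | Null mean | Chance of 0.06 or more | Chance of 0.14 or more |
|---|---|---|---|---|
| 62 | 1 | 0.016 | 6% | 0.3% |
| 62 | 3 | 0.049 | 31% | 3% |
| 62 | 4 | 0.066 | 46% | 7% |
| 62 | 7 | 0.115 | 84% | 29% |
| 50 | 1 | 0.020 | 9% | 1% |
| 50 | 3 | 0.061 | 41% | 7% |
| 50 | 4 | 0.082 | 58% | 14% |
| 50 | 7 | 0.143 | 91% | 46% |
| 30 | 3 | 0.103 | 65% | 26% |
| 30 | 4 | 0.138 | 81% | 42% |

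Simulation agrees: at N = 62 and p = 4 the mean was 0.066, with 0.06 reached in 46.8% and 0.14 in 7.0% of runs. If gender and income share a 2x2 model, the error degrees of freedom are N-4 and the null mean is p/(N-3), slightly worse: 4/59 = 0.068.

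**Relation to the test.** The F test allows for p and N. At N = 62 the 5% critical values of eta squared are 0.125 (p = 3), 0.151 (p = 4) and 0.221 (p = 7). A value of 0.12 would therefore be non-significant in all three cases, yet twice the conventional medium mark.

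**Adjusted form.** 1 - (1 - eta2)(N-1)/(N-p-1). At the null mean for N = 62 and p = 7, this is 1 - (54/61)(61/54) = 0. Its average under no effect is 0.000. The chance of reaching 0.06 at N = 62 falls from 31% to 9% (p = 3), 46% to 11% (p = 4) and 84% to 17% (p = 7). The chance of reaching 0.14 falls from 3% to 1%, 7% to 1% and 29% to 3%.

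**Why an interval is also needed.** The adjustment removes the average bias but not the spread. In the most favourable case, 31 against 31 children (assumed), the 95% half-width for a difference in mean change is t(0.975, 60) x sqrt(1/31 + 1/31) = 2.00 x 0.254 = 0.51 SD.

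**The case against.** The strongest reply is that the SAP does not say the multivariate value is the one reported. If it is the per-outcome value, the null mean at 62 children is 0.016 and the problem largely disappears. That stands, and the point is conditional on it. The missing statement of which value was used is itself a gap, because a reader cannot tell which case applies.

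A reader might infer that the size of subgroup differences rests on eta squared alone, with nothing in scale units. The documents do not support this: raw and estimated marginal means were obtained, and differences follow by subtraction. Only the interval is missing.

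A reader might also infer that a null effect will typically look large. At N = 62 the null mean reaches 0.14 only when p is at least 9 (0.14 x 61 = 8.5). With three or four outcomes, 0.14 is reached by chance in just 3% to 7% of null trials. The p = 7 figures need both outcome families in one model, whereas the SAP names them as two families and speaks of RM-MANOVAs in the plural. The plural could equally mean one model per factor, so neither reading is settled.

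Finally, the SAP neither applies benchmark labels nor says that a non-significant result means no difference. These are follow-on comparisons in a feasibility study, and their p-values are correct as far as this issue goes. All of that stands and limits the weight of the point. It does not remove the case for a better summary at little cost.

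**Conclusion.** The point holds as an inexpensive improvement to the secondary subgroup results. If the multivariate form was used, an absent effect averages about 0.05 to 0.07 with three or four outcomes at the ceiling of 62, and reaches the medium mark by chance in roughly a third to a half of null trials. With seven outcomes, or fewer children analysed, it is worse. If the per-outcome form was used, the bias is small (about 0.02 at N of 50 to 62) and only the missing interval remains. The conclusion rests on assumed values of p, on assumed benchmarks and on the enrolment ceiling standing in for an analysed N that neither document gives. The significance tests and the primary endpoint, change in body weight, are not affected.

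**What to change.** In the SAP:
- For each outcome, add the between-group difference in mean change (boys versus girls, and the two income groups) in scale units with a 95% CI. The point estimates follow from the means already obtained.
- Replace any multivariate partial eta squared with 1 - (1 - eta2)(N-1)/(N-p-1). If gender and income are fitted together in a 2x2 model, use N-3 in place of N-1, giving (N-3)/(N-3-p).
- For each test, state which eta squared is given, the number of outcomes p and the number of children analysed.

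The cost is a few lines of text and a short calculation on existing data. The downside is that the reported effect sizes become smaller.
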